The international single arm CbFAS trial conducted under the original protocol for this study has been completed and the manuscript submitted to Endoscopy journal for publication. See more detail on the preliminary results in separate attachment submitted. In this multicenter, prospective non-randomized trial 39 patients were treated, each subject receiving 1-2 ablations of 6, 8 or 10 seconds. Symptoms were assessed directly and 2 days post-cryoablation. Follow-up endoscopy was performed after 6-8 weeks to assess the ablation response. Outcome parameters were incidence of adverse events, pain, esophageal stricture formation, and ablation response by cryogen dose. *Results*: 56 ablations (10 with 6-sec, 28 with 8-sec, 18 with 10-sec) were performed. Six ablations failed due to device malfunction (n=3) or other reasons (n=3). Median (IQR) procedure time was 7 min (4-10) min. No major adverse events occurred; six patients had a minor mucosal laceration requiring no intervention. Mild pain was reported in 27% of patients immediately after cryoablation and in 14% after 2 days. After 6-8 weeks no strictures had developed. Full squamous regeneration was seen in 6 [60%] of 6s-areas; 23 [82%] of 8s-areas, 100% of 10s-areas). These study results suggest that focal cryoablation of BE with the newly developed CbFAS is feasible, safe, and results in squamous regeneration in the majority of patients. These results were recently published (Scholvinck et al, Endoscopy July 2015 – paper uploaded into eIRB separately)

Furthermore, [name] has treated 41 BE patients and 10 patients with esophageal squamous low grade and high grade dysplasia (neoplasia) within this study and more treated within the clinical cryotherapy program at Johns Hopkins Hospital) with successful ablation in 1-3 outpatient procedures using multifocal cryoballoon ablations, in keeping with standard of care treatment approach to ablation. Research and clinical patients have tolerated cryoablation well, with visible treatment response.

Based upon the results of 2 clinical trials completed under this IRB-approved study,

[name] plans to continue this single center (industry sponsored) study to continue the evaluation of safety, effectiveness and 5-year durability of cryoballoon ablation for esophageal neoplasia.

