### 3.2 Study Purpose and Objectives

**Endpoints:** 

The purpose of this study is to assess the safety, feasibility, performance and the short- and long-term effectiveness of the C2 Focal Cryoablation Device in patients with BE and esophageal squamous dysplasia. Three times of ablation (5, 6, 8, 10 or 12 seconds) can be used and post-ablation symptoms related to the Cryoballoon Focal Ablation will be recorded. At 6 to 12 weeks, the patient will receive a follow-endoscopy to assess stricture formation along with biopsy samples taken.

The ultimate goal is to achieve 90% or greater ablation of BE and 100% ablation of all dysplastic areas.

Post-operative pain will be noted. Additionally, biopsy samples will be evaluated for the presence of residual Barrett's Esophagus. Through evaluation of the histological results, treatment parameters for the ablation of human esophageal epithelium will be better understood.

Evaluations include, but are not limited to the following:

- Deployment ease/scope compatibility.
- Device malfunctions.
- Time of catheter deployment.
- Adverse events.
- Stricture formation at 8 to 12 weeks.
- Patient Pain.
- Histological evaluation of treatment zone at 8 to 12 weeks for presence of residual Barrett's Esophagus.

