**CONFIDENTIAL** 

<sup>3 Stricture formation is defined as none, mild (non-circumferential stenosis allowing easy passage of diagnostic endoscope), moderate (circular stenosis allowing passage of diagnostic endoscope), and severe (any stenosis preventing the passage of a diagnostic scope).

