#### 3.5.3 Stage 3) Patient Follow-up

The follow-up period begins immediately post-procedure. The patient will undergo a follow-up assessment immediately post-procedure / prior to discharge. The patient will undergo a safety phone contact at 1 days (±1 days), 8 (±1 days) days, and 1 month post treatment. Assessment of pain score (0-10 Likert scale), dysphagia score (0-4), odynophagia, diet, medications (including narcotic analgesics) will be performed using a standardized questionnaire.

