### 3.5.4 Stage 4) Follow-up Endoscopy (8 to 12 weeks)

A high definition diagnostic scope can be used during the Follow-up Endoscopy stage unless warranted by institutional guidelines. If there is endoscopically apparent residual BE or squamous dysplasia at the follow-up procedure, this visit will become a treatment visit and cryoablation can be performed.

The Follow-up Endoscopy stage will be as follows:

- Locate and record the gastroesophageal junction (top of gastric folds) by depth of endoscope insertion. Locate, measure, and record the depth of endoscope insertion at the most proximal circumferential extent of suspected columnar metaplasia. Locate, measure, and record the depth of endoscope insertion at the maximum extent of suspected columnar metaplasia or squamous dysplasia. Document the number, localization (insertion depth of the endoscope and orientation in the endoscopic field) of all BE islands.
- 2. Document the location of the top and bottom of the ablation zone (insertion depth of the endoscope and orientation in the endoscopic field). This is done by videorecording or photo documentation and by recording the localization (of the ablated area).
- 3. Evaluate the presence of stenosis at the treatment zone.4
- 4. A biopsy (ies) will be performed according to standard of care, with targeted biopsies sampled from visible mucosal lesions and 4-quadrant random biopsies obtained from the 1 cm distal to the GEJ, the GEJ and every 1 cm proximal to the Z line, or the extent of the original BE or squamous dysplasia. The sample(s) will be collected and submitted as standard of care to Johns Hopkins pathology Thereafter, a representative photo of the biopsy site is taken.

PROTOCOL# CP-0007/ Version: 8 29April 2019

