### 7.3 Safety Related Stopping Rules

The principal investigator will be charged with monitoring the study for safety and for auditing the quality of the data. If there are any perceived safety concerns related to the system or therapy, a corrective action may be implemented or the trial may be terminated.

The principal investigator will meet periodically during the study, after every 10 patients are enrolled and treated, to review any safety concerns. After 20 patients are enrolled and treatments are completed, the DMC will meet to review preliminary efficacy data

Should any of the following occur within 30 days following treatment and be, in the opinion of the investigator, directly attributable to the Therapy or System, the DMC will be alerted as soon as feasible (not to exceed 48 hours of knowledge of the event) and study treatments will be suspended without delay.

- Death or an incident leading to death
- 5 consecutive patients with device malfunctions
- 5 consecutive patients with moderate or severe stenosis in treatment area.

The DMC will review the details surrounding the above-listed event(s) and will be charged with making one of the following decisions:

- Continue without modification to the study protocol or conduct
- Continue with modification

C2 Therapeutics, Inc.

Stop the study

Should the study continue, but with modification (to the System or the study documentation) or if the decision is made to stop the study, the reviewing Ethics Committee(s) and where applicable, the governing agency(ies), will be alerted. Treatments will not commence until the necessary EC approvals for the modification have been obtained.

NOTE: If the decision is made to stop the study, treatments and patient screening activities will cease, however, patient follow up will continue as planned.

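### The stenosis stopping trigger in 7.3 closes at 30 days, before any scheduled endoscopy can grade stenosis, and needs five affected patients in a row, so a steady moderate rate would rarely set it off

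*Combined protocol and SAP*

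**What the plan says.** Section 7.3 opens its list of suspension events with "Should any of the following occur within 30 days following treatment and be, in the opinion of the investigator, directly attributable"; the cause may be either the device or the treatment it delivers. Three items follow: a death, five consecutive patients with device malfunctions, and "5 consecutive patients with moderate or severe stenosis in treatment area". Any of these suspends treatment and alerts the DMC.

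Footnote 3 (attached to the endpoints in 3.1 and repeated in 3.5.4) grades stricture by endoscope passage. Moderate is a circular narrowing that a diagnostic scope still passes; severe is one that it does not.

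On timing, 3.5.3 states "The patient will undergo a safety phone contact at 1 days", with further calls at about day 8 and at one month. Each call covers pain, a 0-4 dysphagia score and painful swallowing. Table 2 adds weekly calls from day 8 to one month, or until resolution, for anyone with symptoms such as pain or dysphagia. Section 3.2 says "At 6 to 12 weeks, the patient will receive a follow-endoscopy to assess stricture formation". Section 3.5.4 puts the follow-up endoscopy at 8 to 12 weeks and there instructs the endoscopist to "Evaluate the presence of stenosis at the treatment zone". Repeat sessions, up to five per patient, are also 8-12 weeks apart (3.5.2 Stage 2, item 12).

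Other safeguards exist. Stricture is a listed complication that must be reported as an AE whatever its severity or incidence (5.2), and each AE gets an onset date (4.0). The principal investigator meets "after every 10 patients are enrolled and treated, to review any safety concerns" (7.3). The DMC may stop or modify the study (6.0), and an unexpected incidence of a known AE is a ground for discontinuation (8.6). None of these names a number of strictures.

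**The concern.** Two features of the trigger work against its purpose. First, its window closes before the protocol's own scheduled assessment of stenosis. Second, it responds to an unbroken run rather than to a total, so it can catch a cluster or a very high rate but not a steady moderate one.

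Adverse events are a primary endpoint (3.1). The current regimen allows up to 24 ablations per session over up to five sessions. If stenosis turned out to be common but not consecutive, the one automatic safeguard would probably stay silent, and any pause would rest on judgement alone.

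**Working it through.** The plan states no operating characteristic for the trigger, so there is no figure to reproduce.

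**Step 1: timing.** The window ends on day 30. The earliest scheduled endoscopy is 6 × 7 = day 42 (3.2), or 8 × 7 = day 56 (3.5.4 and the repeat sessions). The scheduled look therefore comes 12 or 26 days after the window closes.

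**Step 2: chance of a run of five.** Inputs: run length 5 (7.3), up to 100 patients (3.1), and an assumed constant rate p with independent patients. The preliminary-experience section says that the investigator "has treated 41 BE patients and 10 patients with esophageal squamous low grade and high grade dysplasia (neoplasia) within this study". If those 41 + 10 = 51 count toward the 100, then 49 remain; the plan does not say whether they do.

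Let s_j(t) be the probability that, after t patients, no run of five has occurred and the current run has length j (0 to 4). Then:
- s_0(t+1) = (1 − p) × Σ s_j(t)
- s_{j+1}(t+1) = p × s_j(t), for j = 0 to 3
- fired(t+1) = fired(t) + p × s_4(t)

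| Assumed p | Fires, 100 patients | Fires, 49 patients |
|---|---|---|
| 10% | 0.09% | 0.04% |
| 20% | 2.4% | 1.2% |
| 25% | 6.8% | 3.3% |
| 30% | 15.3% | 7.5% |
| 40% | 45.9% | 25.2% |
| 50% | 81.0% | 54.4% |

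Hand check at p = 20%, n = 100: p⁵ × [1 + 95 × (1 − p)] = 0.00032 × 77 = 2.5%, close to the exact 2.4%. The expected number of patients to the first run is (1 − p⁵)/((1 − p)p⁵): 0.99968/0.000256 = 3,905 at 20%, and 0.99757/0.001701 = 586 at 30%.

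**Step 3: incomplete detection by day 30.** Step 2 assumes that every case is found inside the window. If a fraction d is found, p becomes d × p. The documents give no value for d, so a range is shown, over 100 patients:

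| d (assumed) | True rate 20% | True rate 30% |
|---|---|---|
| 1 | 2.4% | 15.3% |
| 0.5 | 0.09% | 0.6% |
| 0.25 | 0.003% | 0.02% |

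**Step 4: what a cumulative count would do.** As an example, assume a tolerated rate of 10%. At each review take the smallest count x with P(X ≥ x | n, 0.10) ≤ 0.02. At n = 10, P(X ≥ 3) = 0.070 and P(X ≥ 4) = 0.013, so the limit is 4. The same rule gives 6/20, 8/30 and 9/40, then 11/50, 12/60, 14/70, 15/80, 16/90 and 18/100. Carrying the binomial distribution forward from review to review, and removing the part that has crossed, gives:

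| True rate | Fires, reviews at 10-40 | Fires, reviews at 10-100 |
|---|---|---|
| 10% | 3.1% | 4.9% |
| 15% | 18% | 37% |
| 20% | 46% | 82% |
| 25% | 73% | 98% |
| 30% | 90% | 99.9% |

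Endoscopy results arrive late. Suppose that 10 more patients are treated before a crossing is known (assumed). With 49 patients, only the reviews at 10-30 can then act before enrolment ends, and the count fires in 31%, 56% and 77% at 20%, 25% and 30%. By simulation (100,000 trials), the mean number affected is then 8.5, 9.4 and 9.7, against 9.8, 12.1 and 14.4 under five-in-a-row with the same lag: about 1, 3 and 5 fewer.

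**The case against.** The strongest reply is that nothing in the documents points to a rate of 20-30%. The only stricture result shown is none among 39 treated patients in the earlier international trial. If all 39 were assessed, the exact 95% upper limit is 1 − 0.025^(1/39) = 9.0%. This stands as a limit on the concern. It does not settle it, because those patients had 1-2 ablations each and the current regimen is much heavier. For later patients the plan says that treatment was well tolerated and cites publications, but it gives no stricture rate.

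A reader might infer that the trigger can never fire. The documents do not support that. Dysphagia is scored at every call, symptomatic patients are called weekly, and either could lead to an endoscopy before day 30. An onset date assigned later could also place a case inside the window. No passage, however, commits to endoscopy for dysphagia.

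A reader might also infer that strictures go unmonitored. They do not: AE recording is mandatory and the 10-patient review is scheduled. Only the response is discretionary. That is partly true of the numeric trigger as well, since after the automatic suspension the DMC may let the study continue unchanged.

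Finally, this is a feasibility study of a cleared device, without a hypothesis, so a formal boundary is one option among several. That is fair as to the exact boundary. It does not answer the mismatch between window and endoscopy.

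**Conclusion.** The concern holds in two parts. The timing mismatch follows directly from the text: the window closes at least 12 days before the first scheduled endoscopy at which the triggering grades can be assigned. The insensitivity is arithmetic: even with complete detection, the trigger fires with probability 2.4% to 15.3% over 100 patients at 20-30%, and reaches about even odds only near 41%. These figures rest on independent patients and a constant rate. The rates are assumed, and so are the detection fractions, the 10% tolerated rate and the 10-patient lag.

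The finding describes how the trigger behaves. It is not evidence that the stenosis rate is high or that patients have been harmed. It is a change worth considering, held with medium confidence because the true rate is unknown.

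**What to change.** In 7.3:

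- For the stenosis trigger only, replace the 30-day window with one that runs through the follow-up endoscopy after each treatment session. Keep 30 days for death and device malfunction.
- Keep five-in-a-row as a guard against clusters, and add a cumulative per-patient count at each existing 10-patient review. The numerator is patients with moderate or severe stenosis after any session. The denominator is all patients with at least one post-treatment endoscopy by that review.
- Suspend treatment and alert the DMC when the count reaches a limit tabulated for every possible denominator, because the number already scoped at a review will not always be a multiple of 10.
- State whether patients already treated are included or the tally starts fresh.

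The sponsor and DMC should set the tolerated rate. The limits 4/10, 6/20, 8/30 and 9/40 are only an example for an assumed 10%.

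The cost is a protocol amendment and a running tally, using endoscopies and reviews already planned. Under the example, an unneeded pause has a 3-5% chance at a true 10%. At a true 15% the count fires about 18% of the time with reviews at 10-40 and 37% with reviews at 10-100. A pause interrupts patients who are mid-course for dysplasia, and detection lag limits how many are spared.

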### 7.4 Missing Data

Missing values will generally be ignored in analyses. Imputation approaches, including last observation carry forward (LOCF) will not be used.

#### 8.0 STUDY MANAGEMENT

As the study Sponsor, Pentax will provide study devices and supplemental funds to continue the trial as a single center study with expanded criteria and adjusted dosing schedule.

[name] is the principal investigator and has the overall responsibility for the conduct of the study.

Study data will be collected using a standardized Case Report Form. The CRF is designed to accommodate the specific features of the trial design.

To ensure proper tracking of Case Report Forms, a master tracking system will be utilized.

## 8.1 Data Management Responsibilities

The Data Management group will employ a relational database to manage and house the resulting study data as collected on the standardized CRF. Conventional data verification routines will be performed. Data Management will be performed according to data audit, data handling and other applicable SOPs.

# 8.1.1Data Entry

Data entry will be performed as the completed CRF pages are received by Data Management. Data entry will be performed by qualified personnel that have undergone appropriate training. Data entry will be verified by a 2nd individual to ensure correct entry. Data entry and verification will be handled according to the applicable data handling and audit procedures.

# 8.1.2Data Cleaning

All CRF pages will be subject to initial inspection for omitted data, gross data inconsistencies, illegible data and deviations. Any deficiencies or deviations will be reviewed and any necessary action determined (e.g., data query, communication to the study center).

## C2 Therapeutics, Inc.

Intermittent data review (including crosschecks) will be performed and any discovered errors will be reported to the study site using the data correction and query process (as necessary). The study site will be expected to review the query, make any necessary corrections or comments, and return to Data Management where the correct response will be entered into the database. The data cleaning cycle will be repeated until all data are considered clean.

#### 8.1.3Data Back-up

Incremental computer data back-up will be performed on a regular basis. All hard copies of Case Report Forms and media will be stored in a secure location.

### 8.1.4Confidentiality and Security

Passwords will be utilized by data entry, data verification and other personnel who have database access to insure confidentiality and protection of data.

#### 8.1.5Data Retention

CRF pages, resolved queries as well as the locked database will be housed in a secure location and will be archived for a minimum of 2 years following commercialization.

CRF pages and queries will be scanned and housed in an organized fashion on a secure server which will be backed up intermittently. The original, hard copy CRFs will remain the original data.

The database will also be managed on a secure server and backed up intermittently per Data Management procedures.

#### 8.2 Ethical Considerations

It is expected that all parties will share in the responsibility for ethical conduct in accordance with their respective roles in the study. The Sponsor and the Investigator(s) shall avoid improper influence or inducement of the subject, monitor, the fellow study Investigator(s) or other parties participating in or contributing to the study.

## 8.3 Data Management Responsibilities

The Investigator will be responsible for Data Management. Data Management will be handled by appropriately qualified personnel.

# 8.3.1 Maintenance of Study Records

The Investigator is responsible for maintaining medical and study records for every subject participating in the study (including information maintained electronically such as digital imaging). The Investigator will also maintain **original** source documents from which study-related data are derived, which include, but are not limited to:

## C2 Therapeutics, Inc.

- Study progress notes recording subject's medical history and medications
- · Medical charts with operative reports and the condition of subject upon discharge
- Medical records regarding AEs, including treatment and clinical outcome
- · Results of diagnostic examinations
- Imaging (such endoscopic images), as well as the report of the reading/interpretation of the images
- Notes of phone calls and/or correspondence indicating investigational site's attempts to follow study subjects until subject's participation in the study is complete or terminated
- Records relating to subject death (e.g., death certificate, autopsy report)
- Print-outs of source data generated by technical equipment (e.g., x-rays, MRIs) must be filed with the patient's records.

The study Sponsor and Investigator must ensure that all study subject records are stored for at least 2 years since the formal discontinuation of clinical development of the investigational product. To avoid error, the study site should contact the Sponsor prior to the destruction of study records to ensure that they no longer need to be retained. In addition, the Sponsor should be contacted if the Investigator plans to leave the investigational site so that arrangements can be made for the handling or transfer of study records.

### 8.3.2 Required Documents from the Investigator

At a minimum, the following documents will be provided by the investigational site to the study Sponsor:

- Signed Investigator Agreement (for each investigator)
- Signed CIP Cover Page
- IRB/EC approval of the study
- IRB/EC approved ICF
- Investigator and Co-Investigator's current signed and dated Curriculum Vitae (CV) \*

A site may not begin study participation until all of the above listed documents have been provided to the study Sponsor.

\* The study may begin once one Investigator for the site has submitted their Investigator Agreement and signed CV. No additional Investigators may participate until a copy of their signed Investigator Agreement and CV has been provided to the study Sponsor.

## 8.4 Training

The System is intended for use by experienced Endoscopists. All Investigators will be provided training by Pentax personnel or designee in the use of the System using a bench top model or equivalent to familiarize them with the use of the System prior to their participation in the study.

### 8.5 Protection of Patient Confidentiality

At all times throughout the study, confidentiality will be observed by all parties involved. All data shall be secured against unauthorized access. Privacy and confidentiality of information about each subject shall be preserved in the reports and in any publication. Each subject participating in this study will be assigned a unique identifier. All CRFs will be tracked, evaluated, and stored using only this unique identifier.

The Investigator will maintain a confidential study subject list identifying all enrolled subjects. This list will contain the assigned study subject's unique identifier and name. The Investigator bears responsibility for keeping this list confidential. This list will not be provided to the study Sponsor and is only to be used at the study center.

NOTE: The subject's name, medical record number or address will NOT be recorded in the sponsor's records, reports or the database; demographic data that may be recorded includes the date of birth, race, and gender.

Any source documents copied by the Sponsor will be identified using the assigned study subject's unique identifier in an effort to protect subject confidentiality.

